10.1 Multiplier method

The multiplier method is based on availability of at least two overlapping data sources specific to the population of interest, one being a count or registry of unique individuals belonging to the population, and another one being a representative survey that assessed whether the participants are present in the first data source. The data sources have to be independent of each other; define the target group in the same way; present the same time period, age and target group geography; be of sufficient data quality.

The formula to calculate the population size using the multiplier method is: $N = M/P$, Where:

N = Estimated Size

P = Proportion of survey participants who reported belonging to the registry (receiving the service, the object, or participating in the survey).

M = Number of individuals in the registry.

The 95% confidence intervals for proportions calculated for descriptive statistics using bootstrapping method with RDS weights will be used to calculate the lower- and upper limits for the population estimates.

The following data sources and indicators will be used for the multiplier method:

#	PSE indicator	Questionnaire item	Existing registry	Data provider
1	Registration in drug treatment clinics	Are you registered with the state narcological clinic in connection with drugs abuse or addiction?	Currently undetermined. Previously: Reporting form No.11 "Report on the morbidity of individuals with mental and behavioral disorders due to psychoactive substance use", annual. Table 2120 "Number of individuals with mental disorders due to intravenous drug use". Indicator: "among people under the supervision at the end of the reporting period".	Regional and city state drug treatment clinics.

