2	Substance use treatment	Were you getting treatment in the state narcological clinic in 2022? (in-patient treatment / out-patient treatment) Have you been getting treatment in the state narcological clinic in 2023 (January-March)? (in-patient treatment / out-patient treatment)	Currently undetermined. Previously: Reporting form No.11 "Report on morbidity of individuals with mental and behavioral disorders due to psychoactive substance use", annual. Table 2300 "Composition of individuals in a drug treatment in-patient clinic". Indicator: "Mental and behavioral disorders due to the use of opioids, cannabinoids, cocaine, hallucinogens, combinations of several drugs and other psychoactive substances, total" Currently undetermined. Previously: Form No.11 "Report on the morbidity of individuals with mental and behavioral disorders due to psychoactive substance use", annual. Table 2100 "Contingent and treatment of individuals with mental disorders due to psychoactive substance use". Indicator: "Mental and behavioral disorders due to opioid use – covered with in-patient/out-patient treatment". Includes data on the number of people registered with a substance abuse clinic, who have already completed in-patient treatment at the end of the reporting period, including those, who have been treated at day drug treatment in-patient clinics.	Regional and city state drug treatment clinics.
3	Criminal	Have you been detained by the police in 2022?	Number of people notified of suspicion under articles	Statistical data

	prosecution	Have you been detained by the police in 2023?	307 and/or 309 during 2019 and 2023. Identified people who committed criminal offences under articles 307 and/or 309 during 2022 and 2023. Committed criminal offences under the influence of drugs, toxic and psychotropic substances under articles 307 and/or 309 during 2022 and 2023.	of the city police and the prosecutor's office.
4	Medications for opioid use disorder (MOUD) coverage	Have you received methadone or buprenorphine within the MOUD program in 2022? Are you taking methadone or buprenorphine within the MOUD program (January-March 2023)?	Number of people who were receiving MOUD in all city medical facilities during 2022. Number of people who were receiving MOUD in all city medical facilities during January-March 2023.	Public Health Center

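### The criminal-prosecution multiplier (Section 10.1, row 3) divides counts limited to articles 307/309 by the share reporting any police detention, and part of one count is for 2019, a year no question covers

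*Protocol*

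**What the plan says.** Protocol Section 10.1 sets N = M/P. It defines P as "Proportion of survey participants who reported belonging to the registry" and gives "M = Number of individuals in the registry". Among its conditions, the two data sources must "define the target group in the same way; present the same time period, age and target group geography". It also describes the first source as a count or registry of unique individuals who belong to the population.

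Row 3 of the multiplier table (criminal prosecution) has two questionnaire items: "Have you been detained by the police in 2022" and "Have you been detained by the police in 2023". Neither is limited to an offence or article.

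The registry column lists three counts from city police and prosecution statistics:

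1. "Number of people notified of suspicion under articles" "307 and/or 309 during 2019 and 2023";
2. people identified as having committed offences under the same articles, 2022 and 2023;
3. offences under the same articles committed under the influence of drugs or similar substances, 2022 and 2023.

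Section 10.4.1 drops city estimates below NGO prevention coverage or above 4% of the adult population. Section 10.4.2 combines the rest by overlap of ranges and averaging, and by an anchored multiplier in which narrower intervals carry more weight.

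**The concern.** M/P estimates the population size only if the people counted in M are the same kind of people, in the same period, as those who answer yes to the question behind P. In row 3 they are not. A person may be detained for reasons unrelated to articles 307 or 309, and nothing in the protocol says that everyone notified of suspicion was detained. People in the counts need not inject drugs.

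Population size is a stated objective (Section 3.0). The consensus city sizes are treated as final and carried into further calculations (Section 10.4.2). City sizes are to weight the pooled and trend estimates once available (Sections 9.2 and 9.4), and the latest size estimate is multiplied by HIV prevalence to give the number of people who inject drugs and live with HIV (Section 9.6). A mismatched input therefore reaches beyond the size table.

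**Working it through.** The protocol states no M, P or N for this row, so there is no figure to reproduce. The check is a comparison of the two columns, followed by an illustration of what a mismatch does to M/P.

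**Comparison with the conditions in Section 10.1**

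| Condition | Questions (P) | Count 1 | Count 2 | Count 3 |
|---|---|---|---|---|
| Same event | any detention | suspicion, 307/309 | identified offender, 307/309 | offence under the influence, 307/309 |
| Same years | 2022; 2023 | 2019; 2023 | 2022; 2023 | 2022; 2023 |
| Limited to people who inject | yes (survey eligibility) | not stated | not stated | not stated |
| Unique persons | yes | yes | yes | worded as offences |

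The event differs for all three counts. The year differs only for the 2019 part of count 1. There is one P per year, shared by every count for that year, so counts of different size give different values of N and at most one of those values can be right. By contrast, row 4 (medications for opioid use disorder) names the same service and the same periods in both columns.

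**Effect on M/P.** Let a be the share of people who inject drugs that the count includes, d the share reporting any detention, and f the share of the count who do not inject. Then M = N × a/(1 − f) and P = d, so

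estimate / N = (a/d) × 1/(1 − f).

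If a 2019 count is divided by the 2022 share, multiply further by M(2019)/M(2022).

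With an assumed true N of 10,000, and assumed ratios because the documents give none, each error taken alone gives:

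- Event: a/d = 0.75, 0.50, 0.25 gives 7,500, 5,000, 2,500.
- Year: M(2019)/M(2022) = 0.5, 0.8, 1.25, 2.0 gives 5,000, 8,000, 12,500, 20,000.
- Non-injectors: f = 0.2, 0.5 gives 10,000/0.8 = 12,500 and 10,000/0.5 = 20,000.

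Combined errors can cancel or reverse: a/d = 0.50 with f = 0.5 gives 0.50 × 2 = 1.0, and a/d = 0.75 with f = 0.5 gives 0.75 × 2 = 1.5, or 15,000.

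**What the screen catches.** Section 2.0 puts national needle and syringe programme coverage at 60%. If NGO coverage in a city were similar (an assumption), the floor would be 0.6 × 10,000 = 6,000. The values 2,500 and 5,000 would be dropped; 7,500 would stay. The ceiling cannot be computed, because the protocol gives no adult populations.

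**What the weighting sees.** With M fixed, the relative standard error of the estimate is about that of P: sqrt(3(1 − P)/(500P)), using n = 500 and the design effect of 3.0 from Section 4.4. That design effect was derived for HIV prevalence and viral suppression, so its use here is an assumption.

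- P = 0.20: sqrt(3 × 0.80/100) = sqrt(0.024) = 0.155.
- P = 0.05: sqrt(3 × 0.95/25) = sqrt(0.114) = 0.338.

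If the broader question attracts more yes answers than a matched one would, the interval narrows and the mismatched estimate gains weight.

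**The case against.** The strongest defence is that the plan limits the damage. Row 3 is one of 11 multiplier rows, used alongside capture-recapture and successive sampling. Implausible estimates are removed under Section 10.4.1, and looking for the overlap of the largest number of ranges restrains an outlier. The year 2019 may be left over from an earlier round. The full questionnaire is not shown and could contain a follow-up on the reason for detention. Section 7.4 also keeps core questions stable so that trends can be followed.

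Most of this bears on severity, and to that extent it stands. It does not make the row valid. The screen removes only values outside the range, and averaging and precision weighting still let an in-range value act. The table that fixes the indicator lists no follow-up item. The data-verification note after the table concerns service coverage indicators, which row 3 is not.

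Three stronger readings are tempting but unsupported:

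- A reader might infer a large underestimate. Assuming 20% detained and 4% in the registry gives 0.04/0.20 = 0.2, or 80% too low. Those inputs are not in the documents, such a value would probably fall below the Section 10.4.1 floor, and non-injectors in the count push the other way.
- A reader might infer that the whole row has the wrong years. Only the 2019 part of count 1 does.
- A reader might infer that six estimates per city enter the consensus. Year-matched pairs number five (one for count 1, two each for counts 2 and 3), and the protocol does not say that each becomes a separate estimate.

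**Conclusion.** The point holds. As written, row 3 fails the protocol's own matching conditions: on the event and the target group for all three counts, on the period for the 2019 part of the first, and apparently on unique persons for the third. M/P from this row does not estimate the number of people who inject drugs.

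The net direction and size of the bias cannot be stated; the figures above only show that it can be material either way. The bootstrap interval for P covers sampling error, not this mismatch, so neither the screen nor the weighting can be relied on to catch it.

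This should be fixed, but it is not critical to the survey. It affects one input among several to the size consensus, and the HIV prevalence and viral suppression proportions within each city do not depend on it. The conclusion rests on the table as printed, without sight of the full questionnaire.

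**What to change.** 1. Reconcile 2019 with 2022 in the first count, and state the same cut-off for 2023 in both columns.
2. Choose one registry count of unique persons and pair it with a question on that same event and period. Alternatively, keep the existing question and request a count of persons detained in the city in the same years.
3. If the questionnaire can no longer change, so that no match is possible, or if the count cannot be limited to people who inject drugs, leave row 3 out of Sections 10.4.1 and 10.4.2 and report it descriptively.

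The cost is one corrected data request and possibly one reworded item, or one fewer input to the consensus. Rewording loses some comparability with earlier rounds, and under Section 6.2 may need ethics re-review if it requires a protocol change. Asking about a specific criminal article may also bring recall and sensitivity problems, which is a reason to consider the matching detention count or the descriptive option first.

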- **Kyiv (fast track city, capital, northern sub-region, largest PWID population)**
- **Dnipro (fast track city, eastern sub-region, high IDU prevalence)**
- **Odesa (fast track city, southern port city, sensitive to new drug use trends)**
- **Kharkiv (north-eastern sub-region, on drug trafficking route from neighboring country, low HIV prevalence)**
- **Cherkasy (central sub-region, high HIV prevalence)**
- **Lviv (western sub-region, on drug trafficking route to/from EU, sensitive to European trends)**

Key characteristics of the selected cities are presented in the Annex. Selection of cities for the 2023 PWID IBBS **on page 55.**

Given the budget allocation for the 2023 IBBS, additional cities will be selected for participation by the national IBBS working group. Similarly to the 2020 round, the selection will be done by a working group based on programmatic and epidemiologic considerations. Possible reasons for selection include not being included in the recent IBBS rounds, assessment of impact of city-level interventions, evidence of outbreaks or unusual behaviors based on other data sources (e.g. SEM, other studies). For the 2023 round, an important priority will be to assess the situation in cities most affected by the war (previously occupied and/or severely damaged). The following cities will be considered as **additional** sites:

- Vinnitsa. (center, less affected by war, significant inbound migration, not included in the 2020 round). *At a meeting of the IBBS working group (June 16, 2023), Vinnytsia was chosen instead of Kherson (by a vote of IBBS working group members). After the Kakhovka dam on the Dnieper River was damaged by Russians, there're some difficulty to conduct IBBS in Kherson (regional team and participant's safety, other difficulties).*
- Zaporizhzhia (south, near the front line, significant out-migration, not included in the 2020 round)
- Chernihiv (north, heavily damaged, not included in the 2020 round)
- Rivne (west, less affected by war, significant inbound migration, not included in the 2020 round)

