5	Harm reduction coverage	Are you a client of any NGO working with people who inject drugs (have a client's card or an individual code)? Have you received free sterile needles/syringes from a non-governmental organization within the last 12 months (March 2022-March 2023)? Have you received free condoms from a non-governmental organization within the last 12 months (March 2022-March 2023)? Have you received HIV testing services from a non-governmental organization within the last 12 months (March 2022-March 2023)?	Number of PWID who received any harm reduction services in March 2022-March 2023.	SYREX database
6	Needle and syringe program coverage	Have you received sterile needles/syringes from a non-governmental organization within the last 3 months (January-March 2023)?	Number of PWID who have received syringes/needles within NGO network (average indicator for 3 months).	SYREX database
7	Condom programming coverage	Have you received condoms from a non-governmental organization within the last 3 months (January-March 2023)?	Number of PWID who have received condoms within NGO network (average indicator for 3 months).	SYREX database
8	HIV testing coverage	Were you tested with a rapid test for HIV in non-governmental organization in 2022? Were you tested with a rapid test for HIV in non-governmental organization in 2023 (January-March)?	Number of PWID who have been tested with the HIV rapid tests for 2022 and 2023 (separately for each year).	SYREX database
9	HCV testing	Did you get a rapid test for hepatitis C at NGO	Number of PWID who have been tested with the HCV	SYREX

	coverage	in 2022? Did you get a rapid test for hepatitis C at NGO in 2023 (January-March)?	rapid tests for 2022 and 2023 (separately for each year).	database
10	HBV testing coverage	Did you get a rapid test for hepatitis B at NGO in 2022? Did you get a rapid test for hepatitis B at NGO in 2023 (January-March)?	Number of PWID who have been tested with the HBV rapid tests for 2022 and 2023 (separately for each year).	SYREX database
11	Syphilis testing coverage	Did you get a rapid test for syphilis at NGO in 2022? Did you get a rapid test for syphilis at NGO in 2023 (January-March)?	Number of PWID who have been tested with the syphilis rapid tests for 2022 and 2023 (separately for each year).	SYREX database

These data will be collected for both IBBS and non-IBBS regions, to enable extrapolation of estimates.

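### Multiplier rows 3, 6 and 7 pair a survey question with a registry count of a different event or measure, contrary to the matching rule in section 10.1

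*Protocol*

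**What the plan says.** Section 10.1 sets the conditions for the multiplier method. The two sources must be independent and must "define the target group in the same way; present the same time period, age and target group geography". The estimator is N = M/P, with M the registry count and "P = Proportion of survey participants who reported belonging to the registry". The confidence limits for N come from the bootstrap interval for P.

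The table in the same section fixes the pairings:

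- **Row 3 (criminal prosecution).** The first question is "Have you been detained by the police in 2022"; the second asks the same about 2023. Neither names an offence. The registry cell lists three counts, all tied to articles 307 and 309: notices of suspicion, identified offenders, and offences committed under the influence of drugs. The first is dated "307 and/or 309 during 2019 and 2023"; the other two are dated 2022 and 2023. None is restricted to people who inject.
- **Rows 6 and 7 (syringes, condoms).** The question asks about receipt "within the last 3 months (January-March 2023". For syringes, M is "Number of PWID who have received syringes/needles within NGO network (average indicator for 3 months"; row 7 uses the same construction for condoms.
- **Row 4 (MOUD), for comparison.** It states 2022 and January-March 2023 on both sides.

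Two later checks apply. The note under the table looks for rapid changes and double counting in service data. Section 10.4.1 drops estimates below the number covered by NGO prevention services or above 4% of adults aged 15-59.

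**The concern.** If the question and the registry describe different events, P is not the probability of being in M, and M/P does not estimate the population size. In row 3, someone detained for an unrelated reason enters P but not M, while someone notified under these articles who does not inject enters M but can never enter P. In rows 6-7, P is cumulative over three months, whereas M is an average.

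The interval reflects only sampling error in P, so it cannot show this bias. Section 10.4.2 gives narrower intervals more weight in the consensus and treats the result as final. City sizes then feed the weighting in sections 9.2 and 9.4 and the number of PWID living with HIV in section 9.6.

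**Working it through.** The protocol gives no M or P, so there is no figure to reproduce. The check is the ratio of estimated to true N. Values of s, f, k, P and city-level coverage below are assumptions.

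**Row 3, definition.** Let D be the number of PWID detained, so P = D/N. Let s be the share of those detained PWID who appear in the registry count, and f the share of that count who are PWID. Treat every PWID in the count as also detained. Then f × M = s × D, so M = sD/f and

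N_est = M/P = (sD/f)/(D/N) = N × s/f.

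| s | f | N_est/N |
|---|---|---|
| 0.25 | 1 | 0.25 |
| 0.5 | 1 | 0.50 |
| 0.5 | 0.5 | 1.00 |
| 1 | 0.5 | 2.00 |
| 1 | 0.25 | 4.00 |

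The direction cannot be determined from the documents.

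**Row 3, year.** No survey question covers 2019. A 2019 count set against the 2022 question would further scale N by M(2019)/M(2022), for which the protocol gives no value.

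**Rows 6-7.** Suppose the average is a monthly mean and each client is served in k of the three months on average. Then M = (k/3) × unique clients, and N_est/N = k/3:

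- k = 1: 0.33
- k = 2: 0.67
- k = 2.5: 0.83
- k = 3: 1.00

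**Would the interval show it?** Take 500 × 0.95 = 475 usable records and design effect 3.0 (section 4.4), with P = 0.30 assumed. The standard error is √(3 × 0.30 × 0.70/475) = 0.0364, so P runs from 0.229 to 0.371 and the interval for N from 0.808 to 1.312 times the estimate.

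- k = 2: 0.667 × 0.808 = 0.539 to 0.667 × 1.312 = 0.875 of true N. The interval misses the true value.
- k = 2.5: 0.833 × 0.808 = 0.673 to 0.833 × 1.312 = 1.093. The interval covers it.

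**Would the range check catch it?** Section 2.0 gives NGO syringe-programme coverage of 60%. If a city sits at that level, the floor is 0.60 N, and an estimate is dropped only when k/3 < 0.60, that is k < 1.8. Then k = 1 is removed, but k = 2 and k = 2.5 pass.

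**The case against.** Several stronger readings are tempting, and the documents do not carry them.

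- **Row 3 understates N.** This would need everyone in the article 307/309 counts to be PWID (f = 1). Nothing in the row says so, and non-PWID in M push N up.
- **Row 3 is out of period altogether.** Two of its three counts match the survey years. The 2019 date looks like a stray or carried-over year. It is still current text that defines a data request, so it needs correcting, but on its own it is an editorial matter.
- **The windows in rows 5-7 are mismatched because a city was chosen late.** Section 4.3 reports that choice with "At a meeting of the IBBS working group (June 16, 2023". That date records one city replacing another and is not a field-start date. Row 5's service questions and its registry both print March 2022-March 2023, and rows 6-7 print explicit months. What stands is that a relative window and a dated window sit in one question and will disagree for interviews held well after March.
- **Every row is mismatched.** Row 4 agrees on both sides, and the registries for rows 1-2 are marked as not yet determined. The point is confined to row 3 and rows 6-7.
- **Every biased row reaches the consensus.** Section 10.4.1 may remove the most extreme underestimates, and section 10.4.2 also relies on overlap between ranges. This protection is partial, as the k = 2 case shows.

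It is also fair to say that the averaged measure in rows 6-7 is undefined and need not be a monthly mean. That makes the size conditional, but it leaves M not stated as a count of individuals over the question's window.

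**Conclusion.** The point holds for row 3 and for rows 6-7. Row 3 is the firmer case: the survey event and the registry event differ, the registry is not limited to the target group, and one count carries a year that neither the questions nor its neighbours share. Its bias has no determined direction; 0.25 to 4.0 is the range for assumed s and f between 0.25 and 1. In rows 6-7 M is ambiguous. If it is a monthly mean, N is too low by k/3 unless every client is served in all three months, and moderate bias can pass the range check. These sizes illustrate the mechanism and do not estimate the error in any city. A later analysis plan could redefine M or drop a row, but it could not change what participants were asked.

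**What to change.** 1. **Row 3.** Exclude it from the triangulated and consensus estimates unless the question and a count limited to PWID can be matched on the same event and years. Rewording the question to name the articles is not enough: with s = 1 and an all-persons count, the ratio is 1/f, for example 2.0 at f = 0.5. Correct 2019 to agree with the survey years.
2. **Rows 6-7.** Define M as unique clients with at least one receipt in January-March 2023, the window printed in the question.
3. **Rows 5-7.** Delete the relative three-month and twelve-month wording, so that only the dated window used for the SYREX extract remains.

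The cost is low. Dropping row 3 and correcting its year are text edits, rows 6-7 need a changed SYREX query, and the wording edits touch a few questionnaire items that can be settled at the piloting and working-group approval already planned in sections 6.2 and 7.4. Keeping row 3 would cost more, because it needs a PWID-only police count that may not exist.

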4.2 Inclusion and exclusion criteria

Selection criteria and verification methods are described in the table below.

Inclusion criteria	Verification methods
Drug injection within the last 30 days	Self-declaration AND confirmation by healthcare worker (presence of punctures on the participant’s body from injection drug use)
14 years old and older as of the survey period	Self-declaration AND visual control by coupon-manager
Not less than 1 month of residence/work/surveying in the area where	Self-declaration

⁸ Lisa G. Johnston (Tulane University), Keith M. Sabin (UNAIDS), “Sampling hard-to-reach populations with respondent driven sampling”, Methodological Innovations Online (2010), 5(2) 38-48

survey is conducted	
Informed consent to participate in all survey components, namely: (1) questionnaire completion; (2) capillary blood collection with EDTA K3 blood micro containers (microtainers) for further rapid testing for HIV, hepatitis C and syphilis; second HIV diagnostic rapid testing in case of positive results; dry blood spot (DBS) for further testing to detect recent HIV infection and viral load level	Signed informed consent to participate in the survey

Exclusion criteria	Verification methods
Repeated participation in one survey round	Self-declaration OR visual identification of a repeated attempt by coupon-manager
Refusal to participate in one or several survey components	Absence of signed informed consent to participate in the survey
Alcohol or drugs intoxication, which does not allow to understand and answer questions of the questionnaire, and the respondent's behavior threatens his own safety or the safety of others	Visual control by coupon-manager

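### The multiplier items do not ask where the service was received, while the registry is a city count for at least some rows, so movers bias M/P down in cities gaining people and up in cities losing them

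*Protocol*

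**What the plan says.** Protocol section 10.1 estimates the population as N = M/P, where M is the registry count and P the survey proportion reporting that they belong to it. It requires the two sources to "present the same time period, age and target group geography".

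The table of indicators then pairs items with registries:

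- **Row 4 (opioid agonist treatment).** The items are "Have you received methadone or buprenorphine within the MOUD program in 2022" and "Are you taking methadone or buprenorphine within the MOUD program (January-March 2023". The registry for the first is "Number of people who were receiving MOUD in all city medical facilities during 2022", with a matching January-March 2023 count for the second.
- **Row 3 (detention).** The item names no place; the data are law-enforcement statistics, including those of the city police.
- **Rows 5-11.** The source is the SYREX database. Row 5, for instance, uses "Number of PWID who received any harm reduction services in March 2022-March 2023", with no geography printed. The footnote to the table has these service indicators checked for consistency city by city, which implies city counts.
- **Rows 1-2.** The registry is stated to be undetermined at present; the providers are regional and city clinics.

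Section 4.2 admits anyone with "Not less than 1 month of residence/work/surveying in the area where" the survey runs. Section 4.3 describes Rivne as "west, less affected by war, significant inbound migration, not included in the 2020 round", describes Vinnytsia's migration in the same way, and describes Zaporizhzhia as a city that many have left. Vinnytsia was chosen on 16 June 2023; the dated service windows end in March 2023.

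**The concern.** P is measured in people who are in the city at the time of the survey, wherever they received the service. M counts people served in the city during an earlier window. The two agree only if few people moved between the window and the interview. Two separate mechanisms break the match:

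- **Arrivals.** A person served elsewhere in 2022 or early 2023 who then moved in counts as a yes in P but is not in M. P is too large for this M, and N is too low.
- **Leavers.** A person served in the city who has since left is still in M but cannot be sampled. N is too high for the current population.

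The first arises because the item names no place. The second would arise with any wording.

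Section 10 mentions migration only in the 4% upper limit of section 10.4.1, which touches neither M nor P. The footnote in 10.1 deals with double counting and sudden changes in service counts.

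At stake are the city consensus sizes, which section 10.4.2 treats as final. They also weight the pooled and trend estimates (9.2, 9.4), and section 9.6 multiplies the latest size estimate by prevalence to obtain the number living with HIV.

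**Working it through.** **Plan's own figure.** Section 10.1 states no numerical result to reproduce. The precision figure in section 4.4 can be checked. With n = 500 less 5% missing = 475, design effect 3 and proportion 0.5, the half-width is 1.96 × sqrt(3 × 0.25 / 475) = 0.078, against the stated ±8 points.

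**Notation.** N0 is the old city size, L the leavers and I the arrivals since the service window. c0 is service coverage in the city, c1 the arrivals' coverage elsewhere, and s the share of arrivals' service already in the host city's registry. Then:

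- Current size: N = N0 - L + I
- Registry: M = c0·N0 + s·c1·I
- Item with no place: P = [c0(N0 - L) + c1·I] / N
- Item restricted to this city: P = [c0(N0 - L) + s·c1·I] / N

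**Inputs.** N0 is taken from the 2017 column of the Annex for scale only: Rivne 3,500, Zaporizhzhia 7,900. The migration shares, c1/c0 and s are assumptions; none is in the documents.

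**Arrivals only.** Rivne, I = 30% of 3,500 = 1,050, true size 4,550, item as printed:

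| c1/c0 | s | M/P | Bias |
|---|---|---|---|
| 0 | 0 | 4,550 | 0 |
| 0.5 | 0 | 3,957 | -13% |
| 1 | 0 | 3,500 | -23% |
| 1 | 0.5 | 4,025 | -11.5% |
| 1 | 1 | 4,550 | 0 |
| 1.5 | 0 | 3,138 | -31% |

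For example, at c1/c0 = 1.5, P = c0 × (3,500 + 1,575)/4,550 = 1.115·c0, and 3,500/1.115 = 3,138. With equal coverage and s = 0, arrivals of 10% and 50% give -9% (3,500 against 3,850) and -33% (3,500 against 5,250). Restricting the item to this city gives P = c0 × 3,500/4,550 when s = 0, hence M/P = 4,550, the correct size.

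**Leavers only.** Zaporizhzhia: M = c0 × 7,900 and P = c0, so M/P = 7,900 under either wording. With 10% leavers the true size is 7,110 (+11%); with 30% it is 5,530 (+43%).

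**Both flows.** N0 = 3,500, 20% out (700), 30% in (1,050), true size 3,850, equal coverage, s = 0. The item as printed gives 3,500 (-9%), because the two errors partly cancel. The city-restricted item gives 3,500 × 3,850/2,800 = 4,812 (+25%). City wording alone is therefore not a complete repair.

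**Scale against sampling error.** At an assumed P = 0.30, with n = 475 and design effect 3, the half-width is 1.96 × sqrt(3 × 0.21/475) = 0.071. P then runs from 0.229 to 0.371, and N from -19% to +31%. The limits in section 10.1 are built from P alone, so they make no allowance for the mover bias.

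**The case against.** The strongest objections, and what of them stands:

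- **The questionnaire is an annex that is not shown.** It may already ask place of service or length of residence, and the English text is a review translation. This stands as a caveat. But the table in 10.1 is where the protocol defines P, and it names no place.
- **The multiplier is one of three methods.** Successive sampling (10.3) uses no registry, and 10.4.2 triangulates. This dilutes the bias without removing it. The additional cities were not in the 2020 round, so the question on 2020 participation has no local first capture there. Unique objects go to two cities not yet named. The consensus rule favours the overlap of the most ranges, so multiplier indicators sharing one bias can reinforce each other. The NGO floor in 10.4.1 cannot catch it, since dividing that same count by P never falls below it.
- **The short 2023 items are less exposed.** True, and the remedy uses it.

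A reader might also infer more than the documents support:

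- **That M/P simply returns the pre-migration size.** This holds only if movers' coverage elsewhere equalled the city's, they moved after the service and none of it is in the host registry.
- **That items reach back 15 months.** That is the joint span of paired items; each dated item covers about 12 months or three, and generally has its own count.
- **That a displaced person is the typical participant.** Section 4.3 gives no share or date of migration.
- **That all eleven rows are affected alike.** Row 1 asks about current registration, the registries for rows 1-2 are open, and city scope for SYREX is inferred.
- **That city service coverage is also wrong.** Section 13.2 defines it as the proportion of PWID reporting receipt. For people now living in the city, services received elsewhere properly belong in it.

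**Conclusion.** The narrow point holds. As written, the multiplier inputs do not meet the protocol's own matching condition. This is plain for rows 3 and 4 and likely for the SYREX rows, and section 10 has no step that adjusts M or P for people who moved. Arrivals bias the estimate downwards, which concerns Vinnytsia and Rivne; leavers bias it upwards, which concerns Zaporizhzhia. Where both flows are large, the net sign is not fixed.

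The size cannot be determined from the documents. Under the assumptions shown, arrivals of 30% of the old size give anything from no bias to -31%, with -23% at equal coverage. Leavers of 10-30% give +11% to +43%. These are illustrations, not estimates for the named cities. The bias can be as large as the sampling error and falls in cities the protocol itself characterises by migration, so it should be corrected.

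**What to change.** 1. Keep the existing items unchanged for trend purposes. After each yes, add a follow-up asking whether this was in this city, and add one item on months lived in the city, unless the questionnaire annex already has them.
2. For rows whose M is a city count, count in P only those answering yes, in this city. State the geography of M for the SYREX rows, and for rows 1-2 once their registry is settled.
3. In cities with marked migration, use the January-March 2023 windows as the primary multiplier inputs and show the 2022 and 12-month indicators as sensitivity analyses only. Row 4 already has a matching count. Rows 8-11 list 2023 counts by year, so these need extracting for the same three months.
4. Use months in the city to report the share who arrived after each window, so that exposure to the bias is shown from data.
5. State the remaining limitation: people served in the 2023 window who left before fieldwork are still in M, and no wording of the item removes them.

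The cost is a short follow-up to each yes, one residence item, and fewer multiplier inputs in the migration cities, with correspondingly less material for the consensus there. Steps 2 and 3 belong together, because restricting P to in-city answers over a long window overshoots when people have also left.
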